Among pregnant women, a cohort design will be used to compare the incidence of pregnancy outcomes (spontaneous abortion, stillbirth, and preterm birth) among those who were exposed to Pfizer-BioNTech bivalent COVID-19 Vaccine during pregnancy compared with that among those who were unexposed to any COVID-19 vaccine during pregnancy (Figure 2). Similarly, a cohort design will be used to compare the prevalence of birth outcomes (major congenital malformations and small size for gestational age) in infants who were born to pregnant women who were exposed to Pfizer-BioNTech bivalent COVID-19 Vaccine during pregnancy compared with that in infants born to pregnant women who were unexposed to any COVID-19 vaccine during pregnancy (Figure 3). Exposed and unexposed pregnant women will be matched on estimated pregnancy start (date of last menstrual period [LMP]), gestational age at cohort entry (for pregnancy outcomes only), maternal age, and US state (if feasible, or broader geographic region if not feasible). Inverse probability of treatment weighting will be used to account for additional confounders.

[figure not shown]
090177e19f732934\Approved\Approved On: 14-Dec-2023 13:35 (GMT)

Figure 2. Cohort design to assess pregnancy outcomes

COVID-19 = coronavirus disease 2019; LMP = date of last menstrual period.

Figure 3. Cohort design to assess birth outcomes

COVID-19 = coronavirus disease 2019; LMP = date of last menstrual period.

A strength of a cohort design with concurrent unexposed comparators is that, unlike the SCRI design, it can be used to study safety events for which the risk varies substantially over time (such as spontaneous abortion) and/or for which the timing of onset is unknown (such as major congenital malformations and small size for gestational age). The use of a contemporaneous comparator rather than a historical comparator avoids bias due to temporal trends in coding for outcomes. Limitations of the cohort approach include the potential for bias due to misclassification of exposed individuals as “unexposed” comparators and bias due to confounding when comparing exposed with unexposed pregnant women.

Confounding will be handled by matching and inverse probability of treatment weighting.

To assess the feasibility for planned analyses, a monitoring analysis will be conducted to describe vaccine utilization among the overall population, among immunocompromised

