9.2.2. Pregnancy outcomes (spontaneous abortion, stillbirth, and preterm birth)

Separate cohorts of pregnant women exposed to Pfizer-BioNTech bivalent COVID-19 Vaccine (exposed cohort) and pregnant women not exposed to any COVID-19 vaccine (unexposed cohort) will be formed for the final analysis of pregnancy outcomes (Table 1). To be eligible for either cohort, pregnant women must be enrolled from 12 months before cohort entry (ie, the index date) until the end of pregnancy.

Table 1. Cohort definitions for analysis of pregnancy outcomes

Cohort	Eligibility criteria	Index date
Exposed cohort	
 Receipt of a dose of Pfizer-BioNTech bivalent COVID-19 Vaccine in the exposure window (as defined in Table 3) Continuous enrollment in the 12 months before the index date until end of pregnancy 	
 Date of vaccination
Unexposed cohort	
 No receipt of any COVID-19 vaccine in the exposure window (as defined in Table 3) Continuous enrollment in the 12 months before the index date until end of pregnancy Matched individually (in a ratio of at least 1:1) to exposed women on estimated pregnancy start (LMP, within pre-specified calendar intervals), maternal age, and US state (if feasible, or broader geographic region if not feasible) 	
 Equivalent of the gestational age at vaccination (in days) in the exposed match. For example, if an exposed individual was vaccinated at 28 weeks and 3 days of gestation, the index date for unexposed matches would be set to 28 weeks and 3 days after their LMP.

COVID-19 = coronavirus disease 2019; LMP = date of last menstrual period; US = United States.

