9.2.4.2. Pregnancy and birth outcomes

For analysis of pregnancy outcomes, pregnant women will be followed from the index date until the earliest of the following: end of pregnancy, latest gestational age at which an outcome can occur (applies only to stillbirth and preterm birth), or receipt of another dose of any COVID-19 vaccine other than Pfizer-BioNTech bivalent COVID-19 Vaccine ([Table 4](#)).

PFIZER CONFIDENTIAL

CT24-WI-GL02-RF02 4.0 Non-Interventional Study Protocol Template For Secondary Data Collection Study
 01-Jun-2022

For analysis of birth outcomes, infants will be followed for events from birth until 12 months after birth (for major congenital malformations) or until 1 month after birth (for small size for gestational age) (Table 4).

Table 4. Follow-up for pregnancy outcomes and birth outcomes

Safety event	Start of follow-up	End of follow-up
Pregnancy outcomes		
Spontaneous abortion	Index date (as defined in Table 1)	Earliest of the following: 
 • Occurrence of spontaneous abortion • 20 weeks of gestation (latest gestational age at which a spontaneous abortion can occur) • Other event marking the end of pregnancy (ectopic pregnancy or pregnancy termination); to be treated as competing events • Receipt of another dose of COVID-19 vaccine other than Pfizer-BioNTech bivalent COVID-19 Vaccine
Stillbirth	Index date (as defined in Table 1)	Earliest of the following: 
 • Occurrence of stillbirth • Other event marking the end of pregnancy (ectopic pregnancy, spontaneous abortion, pregnancy termination, or livebirth); to be treated as competing events • Receipt of another dose of COVID-19 vaccine other than Pfizer-BioNTech bivalent COVID-19 Vaccine
Preterm birth	Index date (as defined in Table 1)	Earliest of the following: 
 • Occurrence of preterm birth (ie, livebirth before 37 completed weeks of gestation) • 37 weeks of gestation (latest gestational age at which a preterm birth can occur) • Other event marking the end of pregnancy (ectopic pregnancy, spontaneous abortion, pregnancy termination, stillbirth); to be treated as competing events • Receipt of another dose of COVID-19 vaccine other than Pfizer-BioNTech bivalent COVID-19 Vaccine
Birth outcomes		

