Comorbidities (in the 12 months before the index date); separate variables for the following conditions: 
 • History of anaphylaxis • History of vaccine-related allergies • Diabetes (type 1 and type 2) • Hypertension • Cardiovascular disease • Cerebrovascular diseases • Chronic respiratory disease • Chronic kidney disease • Chronic liver disease • Cancer • Epilepsy • Infections • Connective tissue disorders • Thyroid disorders • Mood disorders • Asthma • Obesity (capture anticipated to be incomplete in the data sources) 		X		X
Healthcare utilization in the 12 months before or on the index date		X		X
Alcohol abuse and smoking in the 12 months before or on the index date (capture anticipated to be incomplete)		X		X
Reproductive history (in all data available before the index date; if feasible in the data sources): 
 • Spontaneous abortions in previous pregnancies • Pregnancy terminations in previous pregnancies 		X		X
Pregnancy complications during the current pregnancy ^d : 
 • Multiple pregnancy • Gestational diabetes • Preeclampsia/eclampsia • TORCH infections 		X		X
Teratogenic medications (from 28 days before pregnancy start until end of pregnancy ^d)		X		X

090177e19f732934\Approved\Approved On: 14-Dec-2023 13:35 (GMT)

Table 7. Covariates used for descriptive analysis, matching or propensity score estimation

Variable	General safety events	Pregnancy and birth outcomes		
	Descriptive	Descriptive	Matching	Propensity scores

COVID-19 = coronavirus disease 2019; LMP = date of last menstrual period; TORCH = toxoplasmosis, other (syphilis, varicella-zoster, parvovirus B19), rubella, cytomegalovirus, and herpes infections.

a. To be assessed on the index date for general safety events and on LMP for pregnancy and birth outcomes.

b. To be assessed on the index date for analysis of general safety events and from 28 days before LMP until end of pregnancy for pregnancy and birth outcomes. Only information up to and including the index date will be included in propensity scores.

c. Applies only to pregnancy outcomes analysis.

d. Except for multiple pregnancy, only information up to and including the index date will be included in propensity scores.

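### Pregnancy-outcome follow-up starts at the vaccination visit for exposed women but on a calculated gestational day for comparators, and nothing handles losses or preterm labour already under way, so the HR may be biased downward

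*Protocol*

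**What the plan says.** Table 1 (Section 9.2.2) gives the exposed cohort the vaccination date as index date. The comparator's index date is defined as "Equivalent of the gestational age at vaccination (in days) in the exposed match", counted from her own LMP. In the table's own example, where the exposed woman was vaccinated at 28 weeks 3 days, "the index date for unexposed matches would be set to 28 weeks and 3 days after their LMP". Section 9.2.4.2 then says that "pregnant women will be followed from the index date until the earliest of the following", and Table 4 starts follow-up for spontaneous abortion, stillbirth and preterm birth on the index date, with no lag.

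Three provisions bear on comparability at that moment:

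- **Matching.** Section 9.1 lists estimated pregnancy start, "gestational age at cohort entry (for pregnancy outcomes only), maternal age, and US state".
- **Eligibility.** Both cohorts need "Continuous enrollment in the 12 months before the index date until end of pregnancy". Neither cohort has a criterion about warning signs at index.
- **Propensity score.** Table 7 includes "Pregnancy complications during the current pregnancy", specified as gestational diabetes, preeclampsia or eclampsia, TORCH infections and multiple pregnancy. Apart from multiple pregnancy, only information up to the index date is used.

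The cohort sensitivity analyses in Table 10 are restriction to registry-linked women, restriction to women with recorded monovalent vaccination, and bias analyses for exposure and outcome misclassification.

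**The concern.** The two index dates match in gestational age but not in what they imply about the pregnancy. An exposed woman chose to attend for a vaccine that day. Nothing comparable is known of the comparator. A woman who is bleeding, has been told the fetus is not viable, or is being seen for threatened preterm labour may well postpone vaccination. If she does, she cannot be exposed at that gestational age, but she can be someone's comparator, and her loss or preterm birth then falls early in comparator follow-up.

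Estimating the relative risk of these outcomes is a primary safety objective, and the likely error runs toward making the vaccine look safer. The mechanism does not depend on how vaccination after the index date is handled. The requirement of "No receipt of any COVID-19 vaccine in the exposure window (as defined in Table 3" for comparators is a separate matter and is not relied on here.

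**Working it through.** **1. The plan's own figures.** Table 9 is not in error. For stillbirth (0.5%, HR 1.2, 100,000 per group), expected events are 100,000 × (0.005 + 1 − 0.995^1.2) ≈ 1,100. Schoenfeld power is Φ(½√1,100 × ln 1.2 − 1.96) = Φ(1.06) = 0.856, against 0.851 in the table. These calculations assume that the HR is estimated without bias.

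**2. Does any listed control reach the mechanism?**

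| Provision | What it controls | Acute warning signs at index? |
|---|---|---|
| Matching (9.1, Table 1) | calendar time, gestational age, maternal age, region | No |
| Enrolment to end of pregnancy (Table 1) | should keep out pregnancies recorded as ended before index | No |
| Propensity score (Table 7) | comorbidity, utilisation, four named complications | No code for threatened loss, bleeding, non-viability or threatened preterm labour |
| Prior-monovalent restriction (9.7.3.3) | stable health-seeking behaviour | No |
| Other Table 10 analyses | exposure and outcome misclassification | No |

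**3. Illustration for spontaneous abortion, true HR 1.0.** From the protocol: 12% incidence, 20,000 per group (9.5.2), and an exposure window from 28 days before LMP to 19w6d, which is day 139 (Table 3). Assumed, because the documents give nothing: losses occur on days 35 to 139 with total hazard H = −ln(0.88) = 0.128, either constant or declining exponentially on a 30-day scale (front-loaded); vaccination is spread evenly over the stated days; deferral removes a fraction d of exposed events in the first L days.

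For index day g, let S(g) be the probability that the pregnancy is ongoing, C(g) the hazard from g to day 139, and E(g,L) the part of it in the first L days. Then

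HR = Σ S(g)[C(g) − d·E(g,L)] / Σ S(g)C(g)

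95% half-width on log HR = 1.96 × √(2 / (20,000 × C̄)), where C̄ = ΣS·C / ΣS.

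| | Days −28 to 139, constant | Days −28 to 139, front-loaded | Days 35 to 139, constant | Days 35 to 139, front-loaded |
|---|---|---|---|---|
| d = 25%, L = 7 | 0.986 | 0.981 | 0.969 | 0.942 |
| d = 50%, L = 7 | 0.971 | 0.963 | 0.937 | 0.884 |
| d = 50%, L = 14 | 0.942 | 0.925 | 0.878 | 0.793 |
| C̄ | 0.090 | 0.0715 | 0.066 | 0.034 |
| Half-width | 0.065 | 0.073 | 0.076 | 0.106 |

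Over the protocol's window, one of the six scenarios is significant at 5% (ln 0.925 = −0.078 against 0.073). With vaccination on days 35 to 139 only, three of six are. A weaker deferral of 10% over 7 days gives 0.98 to 0.99 across all four columns.

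The window matters because 63 of its 168 days (−28 to 34) precede the first day on which this model places a loss. On the 28 days before LMP the mechanism cannot act at all.

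**4. A general form for any of the three outcomes.** Let f be the share of comparator events already under way at index, and e the probability that such a woman is vaccinated anyway. Under a true HR of 1, the observed HR is 1 − f(1 − e), so there is no bias when e = 1. With e = 0 and a true HR of 1.2, the observed HR is 1.2 × (1 − f): 1.18, 1.14 and 1.08 for f = 2%, 5% and 10%. It falls below 1 only if f exceeds 1 − 1/1.2 = 16.7%.

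For stillbirth at 100,000 per group and f = 5%, events are 500 + 570 = 1,070 and power is Φ(½√1,070 × ln 1.14 − 1.96) = 0.57, down from 0.86. It is 0.76 at f = 2% and 0.24 at f = 10%. Neither f nor e is given in the documents.

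**The case against.** Assigning each comparator her match's gestational age is a sound device: it avoids immortal time and, with the enrolment rule, should keep out pregnancies already recorded as ended. Whether a coded missed abortion or fetal demise itself marks the end of pregnancy depends on the algorithm that Section 9.2.1.2 leaves to the SAP. The propensity score contains utilisation, infections and preeclampsia up to the index date, and Section 9.9 concedes residual confounding. Code lists and further sensitivity analyses often sit in a SAP. All of this stands and limits the size. It does not close the gap, because the index dates, the immediate start of follow-up, the covariate list and the table of planned analyses are all fixed in the protocol, and none of them covers acute warning signs.

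Three stronger readings are tempting, and the documents do not support them:

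- **That losses under way fall only in the unexposed arm.** Section 9.9 notes that early losses may go unrecognised even by the woman, and she then has no reason to defer. The imbalance is one of degree.
- **That the HR is pushed below 1.** This follows only if the true HR is near or below 1, or if f is large.
- **That most plausible scenarios would show significant protection or cancel an HR of 1.2.** Using all 2,400 expected losses per arm gives a half-width of 0.057, but many losses precede an index date spread across gestation. With the half-widths above, one of six scenarios is significant over the protocol's window, and the most extreme turns 1.2 into 1.2 × 0.925 = 1.11. Only with vaccination confined to days 35 to 139, front-loaded hazard and 50% removal over 14 days does 1.2 fall below 1 (1.2 × 0.793 = 0.95).

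**Conclusion.** The asymmetry at time zero is written into the protocol, and no listed covariate, eligibility rule or sensitivity analysis addresses it. The likely direction is downward, which matters for a primary safety objective. The size is unknown. For spontaneous abortion under a true HR of 1.0 and the assumed deferral, it is about 0.93 to 0.99 over the protocol's exposure window (half-width about 0.07) and about 0.79 to 0.97 if vaccination falls only on days 35 to 139 (half-width about 0.08 to 0.11). These ranges rest on assumed deferral fractions, durations, hazard shapes and vaccination timing. No comparable time-based model was run for preterm birth or stillbirth. For preterm birth the issue is labour or complications under way rather than loss, and preeclampsia recorded by index is already in the score. This is a worthwhile, inexpensive improvement; it does not invalidate the design.

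**What to change.** 1. **Table 7.** Add to the propensity score current-pregnancy codes recorded on or before the index date for threatened, missed or inevitable abortion, bleeding and fetal demise, and for the preterm-birth analysis threatened preterm labour. Alternatively, exclude women with such codes from both cohorts in Table 1.
2. **Table 10.** Add a pre-specified sensitivity analysis that starts follow-up a fixed number of days after index (for example 8 and 15) in both arms, among pregnancies still ongoing then. Report it beside the unchanged primary HR.

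The cost is a short code list and one rerun of the same program. The data are secondary, and Section 6 places the final query in the second quarter of 2026. If exclusion is chosen, slightly fewer pregnancies remain. The lagged analysis cannot see an effect in the first days, and it reduces the bias without removing it, because a recognised complication can lead to an event later than the lag. For that reason both steps are needed, and the lagged result should supplement the primary.

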9.2.3. Birth outcomes (major congenital malformations and small size for gestational age)

Separate cohorts of pregnant women exposed to Pfizer-BioNTech bivalent COVID-19 Vaccine (exposed cohort) and pregnant women not exposed to any COVID-19 vaccine (unexposed cohort) will be formed for the analysis of birth outcomes (Table 2). To be eligible for either cohort, women must have had a singleton pregnancy ending in a livebirth and must have had continuous enrollment from 12 months before the index date until birth. The index date in both exposed and unexposed women will be the LMP date. Analyses will be limited to pregnant women whose singleton pregnancies have ended in a livebirth and who have been successfully linked to an infant.

Table 2. Cohort definitions for analysis of birth outcomes

Cohort	Eligibility criteria
Exposed cohort	
 Pregnancy ending in a livebirth, with continuous enrollment in the 12 months before the index date (LMP) until birth Pregnancy linked to at least 1 infant Receipt of Pfizer-BioNTech bivalent COVID-19 Vaccine during the outcome-specific exposure window (as defined in Table 3)
Unexposed cohort	
 Pregnancy ending in a livebirth, with continuous enrollment in the 12 months before the index date (LMP) until birth Pregnancy linked to at least 1 infant

PFIZER CONFIDENTIAL

Table 2. Cohort definitions for analysis of birth outcomes

Cohort	Eligibility criteria
	
 No receipt of any COVID-19 vaccine during the outcome-specific exposure window (as defined in Table 3) Matched individually (in a ratio of at least 1:1) to exposed women on LMP, maternal age, and US state (if feasible, or broader geographic region if not feasible)

COVID-19 = coronavirus disease 2019; LMP = date of last menstrual period. US = United States

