9.2.3.1. Exposure windows for analyses in pregnant women

Outcome-specific exposure windows are provided in Table 3. For pregnancy and birth outcomes, only women who were exposed to Pfizer-BioNTech bivalent COVID-19 Vaccine during outcome-specific exposure windows will be eligible for the exposed cohorts. For each pregnancy and birth outcome, the exposure window will be from 28 days before pregnancy start until the end of the outcome-specific risk period (as defined in [Section 9.3.2.2](#)).

Table 3. Exposure windows for analysis of pregnancy outcomes and birth outcomes

Type of safety event	Safety event of interest	Exposure window
Pregnancy outcomes	Spontaneous abortion	From 28 days before LMP until 19 weeks and 6 days of gestation
	Stillbirth	From 28 days before LMP until pregnancy end
	Preterm birth	From 28 days before LMP until 36 weeks and 6 days of gestation
Birth outcomes	Major congenital malformations	From 28 days before LMP until the last day of the first trimester
	Small size for gestational age	From 28 days before LMP until pregnancy end

LMP = date of last menstrual period.

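### Table 7 lists in-pregnancy propensity-score covariates that the birth-outcome analysis cannot use, because covariate information stops at an index date set to the LMP

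*Protocol*

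**What the plan says.** Section 9.2.3 fixes the birth-outcome index date: "The index date in both exposed and unexposed women will be the LMP date". Table 2 repeats it in the enrollment criterion for both cohorts: "Pregnancy ending in a livebirth, with continuous enrollment in the 12 months before the index date (LMP) until birth". Both cohorts are restricted to singleton live births.

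Table 7 in Section 9.3.3 has a single propensity-score column headed for pregnancy and birth outcomes together. Two of the rows marked in it concern the pregnancy itself:

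- "Pregnancy complications during the current pregnancy", covering multiple pregnancy, gestational diabetes, preeclampsia/eclampsia and TORCH infections.
- "Teratogenic medications (from 28 days before pregnancy start until end of pregnancy".

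Footnote d governs both rows: "Except for multiple pregnancy, only information up to and including the index date will be included in propensity scores". Footnote b applies the same limit to other routine vaccines: "Only information up to and including the index date will be included in propensity scores". History of severe COVID-19, also in the propensity-score column, is taken as of the index date.

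Exposure may occur much later than LMP. For malformations, Table 3 gives the window as "From 28 days before LMP until the last day of the first trimester"; for small size for gestational age it runs to the end of pregnancy. For pregnancy outcomes, by contrast, Table 1 sets the index date at vaccination, or at the same gestational age in the matched comparator.

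**The concern.** Each rule is reasonable alone. Together, for birth outcomes, they close the covariate record on the day from which pregnancy is dated, while the covariate list includes conditions and drug use that arise during pregnancy. A programmer following the text exactly would build a score in which several listed covariates are zero for every woman.

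Section 9.7.2 makes inverse probability weighting the only primary-analysis control for variables that are not matched on, so nothing else recovers them. The planned restriction to women with prior monovalent vaccination is aimed at health-seeking behavior and exposure misclassification, not at these factors. At stake are the adjustment for primary objective 3 and a final report that would list covariates as adjusted when they never entered the model.

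**Working it through.** **Scale of the design.** The protocol gives no figure for this point. For scale, Section 9.5.2 states 90% power for an odds ratio of 1.2 with 3% in the unexposed and 20,000 per group. The exposed risk is then 0.0358, and a two-proportion calculation gives power 0.900. The stated figure is reproduced, and this point does not change it.

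**Which listed covariates survive an LMP cut-off.** Take LMP as day 0, so usable information ends on day 0.

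| Table 7 item | What remains for birth outcomes |
|---|---|
| Gestational diabetes, preeclampsia/eclampsia, TORCH infections (current pregnancy) | Nothing usable; they arise after day 0 |
| Multiple pregnancy | Exempt from the cut-off, but constant in singleton cohorts |
| Teratogenic medications | Days -28 to 0 only |
| Severe COVID-19 | History up to LMP; nothing between LMP and vaccination |
| Other vaccines | Days -28 to 0 only (footnote b) |

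Footnote c ("Applies only to pregnancy outcomes analysis") is attached only to gestational age on the index date, so it does not remove the other rows from the birth-outcome score. The abstract says that shared covariates apply as appropriate, but it too singles out only gestational age.

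**Teratogen window.** Usable days: 28 + 1 = 29. The listed window runs to the end of pregnancy. Assuming pregnancy ends at 37w0d (day 259) or 40w0d (day 280):

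- 29 / (259 + 29) = 29/288 = 10%
- 29 / (280 + 29) = 29/309 = 9%

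All days after LMP are excluded, hence essentially the whole first trimester, which Table 6 names as the etiologic period for malformations.

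**Share of the exposure window after the cut-off.** With the last exposure day E counted from LMP, the share is E / (E + 29).

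- Malformations, first trimester assumed to end at 11w6d (E = 83): 83/112 = 74%
- Malformations, ending at 13w6d (E = 97): 97/126 = 77%
- Small size for gestational age, birth at 37w0d: 259/288 = 90%
- Small size for gestational age, birth at 40w0d: 280/309 = 91%

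These are shares of calendar days, not of vaccinations; the protocol gives no distribution of vaccination timing.

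**What a vaccination-date cut-off would recover.** A woman vaccinated on day k contributes k + 29 days of teratogen information. Over a window ending at 13w6d this runs from 1 day (k = -28) to 126 days (k = 97), with mean (1 + 126)/2 = 63.5 if vaccination were uniform over the window (assumed). Women vaccinated before LMP would contribute 1 to 28 days, fewer than now; the days dropped are those after vaccination.

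**Illustrative bias.** For a wholly unadjusted binary factor, bias factor = [1 + p1(RR - 1)] / [1 + p0(RR - 1)], with p1 and p0 its prevalence in exposed and unexposed women. All inputs are assumed:

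- 4% vs 2%, RR 3: 1.08/1.04 = 1.04
- 6% vs 3%, RR 4: 1.18/1.09 = 1.08

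**The case against.** The strongest reply is that an LMP anchor is a legitimate choice. It gives both arms one pre-pregnancy baseline, avoids adjusting for variables that follow vaccination, and is applied consistently in the text and Table 2. That stands as a defense of LMP as the cohort anchor. It does not rescue Table 7, which would then be wrong to list these items for birth outcomes. Nor does an LMP cut-off separate before from after vaccination: it discards pre-vaccination information for women vaccinated later and admits post-vaccination information for those vaccinated in the 28 days before LMP.

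A reader might infer that teratogens are not adjusted for at all. The text does not support that. Dispensings from day -28 to day 0 enter, so ongoing users who filled in that window are captured, and related conditions (epilepsy, diabetes, hypertension, immunosuppressant use) are separate 12-month covariates. What is lost is use first dispensed after LMP.

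A reader might also compare the 29 days with 126 and call the difference recoverable. It is not: capture should stop at vaccination, and 126 days is reached only by vaccination on the last day of a first trimester ending at 13w6d.

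Moving the whole index date to vaccination would carry costs. It would shift the enrollment requirement and the 12-month lookbacks, in late vaccination mostly into pregnancy. A requirement that the comparator still be pregnant would also have no meaning for vaccinations before LMP. These objections stand, and they argue for a narrower repair.

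**Conclusion.** The contradiction is in the protocol's own text and does not depend on the unseen SAP. Followed exactly, Section 9.2.3 and footnote d leave the birth-outcome propensity score without any current-pregnancy complication, without teratogen use first dispensed between LMP and vaccination, and without severe COVID-19 in that interval, although Table 7 lists all of them. Confounding by factors arising between LMP and vaccination can therefore remain in primary objective 3.

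Its size and direction are unknown. The factors of 1.04 and 1.08 rest on assumed prevalences and risk ratios and treat the factor as wholly unadjusted; they do not show that the odds ratio of 1.2 used in planning would be produced or masked. A reader might also infer immortal-time bias in the small-for-gestational-age analysis from its late exposure window. That is a separate claim that nothing here demonstrates, and this conclusion does not rest on it. The pregnancy-outcome analyses are unaffected, since their index date is vaccination or its matched gestational age.

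**What to change.** Keep LMP as the anchor for enrollment, matching and the 12-month baseline lookbacks. For birth outcomes, add a separate propensity-score cut-off for the in-pregnancy covariates (complications, teratogenic medications, severe COVID-19, other vaccines): the vaccination date in exposed women and the same day relative to LMP in the matched comparator. Counting days from LMP also covers vaccinations before LMP. Amend footnotes b and d, and the timing given for severe COVID-19, accordingly. Multiple pregnancy can be dropped from the birth-outcome score.

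If the LMP cut-off is deliberate, split Table 7 by outcome type, remove these items from the birth-outcome propensity score, and state in the analysis and limitations sections that they are not adjusted for.

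The first option needs no new data and follows the timing rule already in Table 1. It costs a little programming, one extra date per matched set, and a stated rule for a comparator who delivers before her matched day. The second costs wording only, but leaves the confounding in place.
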